- I agree to ensure that all associates, colleagues and employees assisting in the conduct of the study are informed about their obligations. Mechanisms are in place to ensure that site staff receive the appropriate information throughout the study.

Investigator's Approval

Name:	Research Site:	Signature	Date
[name]	ICL		05 DEC 2022

Sponsor's Approval

Name:	Role:	Signature	Date

GLOSSARY OF ABBREVIATIONS

6MWD	6-Minute Walk Distance
6MWT	6-Minute Walk Test
AE	Adverse Event
AR	Adverse Reaction
β-hCG	beta human Chorionic Gonadotropin
BP	Blood Pressure
CRF	Case Report Form
FSH	Follicle Stimulating Hormone
GCP	Good Clinical Practice
ICH	International Conference on Harmonisation
PAH	Pulmonary Arterial Hypertension
PCR	Polymerase Chain Reaction
REC	Research Ethics Committee
SAE	Serious Adverse Event
SAR	Serious Adverse Reaction
SNP	Single Nucleotide Polymorphism
SUSAR	Suspected Unexpected Serious Adverse Reaction
TPR	Total Pulmonary Resistance
WHO	World Health Organisation

Keywords: Pulmonary Arterial Hypertension; PAH; XBD173;

STUDY SUMMARY

TITLE:	Investigating the relationship between endothelial cell activation and total pulmonary resistance (TPR) in pulmonary artery hypertension (PAH)		
PHASE:	IB		
MEDICINAL PRODUCT:	XBD173		
DESIGN:	Open-label, single-centre		
OBJECTIVE(S):	To determine whether changes in endothelial cell dysfunction are associated with changes in total pulmonary resistance in patients with pulmonary arterial hypertension		
INTERVENTION:	XBD173 - oral administration for up to 8 weeks		
EVALUATION MEASURES:	
 1. Change in plasma sVCAM1, e-selectin, GDF-15 and NT-proBNP 2. Change in total pulmonary resistance 		
POPULATION:	Up to 6 individuals with PAH.		
STUDY CENTRES:	Site ID		
STUDY CENTRES:		Site Name	Academic Affiliation
STUDY DURATION:	1000	Royal Hallamshire	University of Sheffield
ELIGIBILITY	
Inclusion criteria:
 
 1. Subjects aged between 18-75 years old 2. PAH which is: idiopathic; PAH heritable; PAH associated with connective tissue disease; PAH after \geq 1 year repair of congenital systemic to pulmonary shunt; or PAH associated with anorexigens or other drugs. 3. Resting mean pulmonary artery pressure \geq25 mmHg, pulmonary capillary wedge pressure \leq15 mmHg, PVR >5 wood units, and normal or reduced cardiac output, as measured by a previous right heart catheterisation (RHC). 4. Have an insertable FDA/CE cardiac rhythm monitor and pulmonary artery pressure monitor that captures cardiopulmonary haemodynamics and daily activity. 5. Six-minute walking distance $>$50m at entry 6. Stable on an unchanged PAH therapeutic regime comprising at least 2 therapies licensed for PAH (any combination of endothelin receptor 		

	
antagonist, phosphodiesterase inhibitor or prostacyclin analogue) for at least 1 month prior to screening
 
7. Subjects willing to be genotyped for genes that influence XBD173 activity
 
8. Able to provide written informed consent prior to any study mandated procedures
 
9. Contraception: Fertile females (women of childbearing potential) are eligible to participate after a negative highly sensitive pregnancy test, if they are taking a highly effective method of contraception other than the oral contraceptive pill during treatment and until the end of relevant systemic exposure -see details in section 4.3.1-
 
Exclusion criteria:
 
 1. Unable to provide informed consent and/or are non-fluent speakers of the English language 2. Hypersensitivity to XBD173 or to any of the excipients 3. Clinically-significant renal disease (confirmed by creatinine clearance <30 ml/min per 1.73m²) 4. Clinically-significant liver disease (confirmed by serum transaminases >2 times than upper normal limit) 5. Anaemia confirmed by haemoglobin concentration <10 g/dl 6. Individuals known to have haemoglobinopathy sickle cell disease, thalassaemia 7. Hospital admission related to PAH or change in PAH therapy within 3 months prior to screening 8. History of left-sided heart disease and/or clinically significant cardiac disease, including but not limited to any of the following: 
 a. Aortic or mitral valve disease (stenosis or regurgitation) defined as greater than mild aortic insufficiency, mild aortic stenosis, mild mitral stenosis, moderate mitral regurgitation b. Mechanical or bioprosthetic cardiac valve c. Pericardial constriction, effusion with tamponade physiology, or abnormal left atrial size. d. Restrictive or congestive cardiomyopathy e. Left ventricular ejection fraction ≤50% (measured in echocardiogram at screening) f. Symptomatic coronary disease g. Significant (2+ for regurgitation) valvular disease other than tricuspid or pulmonary regurgitation h. Acutely decompensated left heart failure within 1 month of screening i. History of untreated obstructive sleep apnoea 9. Evidence of significant lung disease on high-resolution CT (if available) or recent (performed within 12 months) lung function, where FEV1 < 50% predicted and FVC < 70% predicted, and DLCO (or TLCO) < 50% predicted if any CT abnormalities; judged by the
--	--

	
Site Physician
 
10. Patients with a history of uncontrolled systemic hypertension
 
11. Acute infection (including eye, dental, and skin infections)
 
12. Chronic inflammatory disease including HIV, and Hepatitis B
 
13. Women of childbearing potential who are pregnant or breastfeeding (if applicable)
 
14. Patients who have received an Investigational Medicinal Product (IMP) within 5 half-lives of the last dose of the IMP or 1 month (which ever is greater) before the baseline visit
 
15. Use of the following medications or therapies:
 
 • Severe and moderate P450 CY3A4 inhibitors: Boceprevir, Clarithromycin, Cobicistat, Idelalisib, Itraconazole, Ketoconazole, Nelfinavir, Ritonavir, Saquinavir, Telaprevir, Telithromycin, Voriconazoleb, Aprepitant, Conivaptan, Crizotinib, Diltiazem, Dronedarone, Erythromycin, Fluconazole, Imatinib, Isavuconazole, Nefazodone, Netupitant, Nilotinib, Posaconazolee, Tofisopam, Verapamil, Delavirdine. • Severe and moderate P450 CY3A4 inducers: Carbamazepine, Enzalutamide, Fosphenytoin, Mitotane, Phenytoin, Rifampicin, Bosentan, Efavirenz, St John's wort, Barbiturates, Nevirapine, Primidone, Rifabutin, Rifapentine. • Oral contraceptives • Oral anticoagulants or antiplatelet agents other than low dose aspirin • Levothyroxine

PHARMACOLOGICAL CHALLENGE:
	
For the first 2 participants, XBD173 will be given orally 90mg once daily for 8 weeks, in addition to their usually medication.
 
For the next 4 participants, XBD173 will be given orally 90mg once daily for the first 2 weeks, in addition to their usually medication, and then orally 90mg twice daily for 6 weeks.
 
Enrolment will be staggered so that each participant will start dosing at least 2 weeks after the previous participant.
 
Patients will be monitored for safety by clinic visit at the end of Weeks 2, 4, and 8. They will be followed for a further 4 weeks off study treatment.
 
Blood levels of XBD173 will be measured in each patient at the end of Week 8.

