4.1 Overall study design and plan

Patients will be invited to participate by their local pulmonary hypertension hospital. The first 2 participants will be treated with XBD173 90mg once daily for 8 weeks. The first patient will be followed for at least 2 weeks before the second patient starts the XBD173. Subsequent participants will be treated with XBD173 90mg once daily for 2 weeks at intervals of at least 2 week and if the drug is tolerated (defined as an absence of grade 2 adverse events) the dose will be increased to 90mg twice daily for a further 6 weeks. The total period of treatment for each patient is 8 weeks, followed by 4 weeks follow up off XBD173. If a grade 2 AE occurs during 90mg once daily dosing, the participant will be withdrawn. If a patient does not tolerate 90mg twice daily, the local PI will determine whether to stop XBD173, reduce the dose to 90mg once daily or pause dosing and restart at 90mg once daily.

The starting dose of 90mg OD is based on experience from studies of XBD173 in healthy volunteers and in patients with multiple sclerosis.

Rupprecht et al randomised 71 healthy volunteers to 7 days treatment with placebo, 10, 30, or 90 mg/day XBD173 or 2 mg/day alprazolam (PMID: 19541954). The number of side effects reported with XBD173 was comparable to the incidence in the placebo group. In contrast, a much higher incidence was reported by the alprazolam-treated group.

In addition, 4 studies have been sponsored by Imperial College London using XBD173. In all studies XBD173 was well tolerated with no SAEs:

17/LO/0566. This study recruited healthy volunteers (n=31) and people with MS (n=12) and administered XBD173 90mg for 7 days. (To be submitted for publication September 2022).

14/LO/0343. This study recruited people with MS (n=6) and administered a single dose of XBD173 (90mg) prior to PET scanning with 11C-GE180. (PMID: 30796709).

12/LO/0735. This study recruited healthy volunteers (n=6) and administered a single dose of XBD173 ranging from 10mg-90mg prior to PET scanning with 11C-PBR28. (PMID: 24623083).

13/LO/1916. This study recruited healthy volunteers (n=6) and people with MS (n=6) and administered a single doses of XBD173 (90mg) prior to PET scanning with 11C-PBR28. (PMID: 30796709)

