5.4 Treatment assignment

All patients will receive XBD173 at 90mg once daily. Patient 3 onwards will escalating to 90mg twice daily after 2 weeks.

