6.4 Hospital assessment (Week 2 ± 3 days)

Patients will attend for safety, urinary pregnancy test (if indicated) and research blood tests, to check concomitant medications, and for the occurrence of AEs. Following completion of these procedures and review of the blood tests, the physician can increase the dose of XBD173 to 90mg twice daily.

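### The stagger between participants is set by elapsed time alone, so participant 2 may start before any scheduled on-drug blood result exists in the trial

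*Protocol*

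**What the plan says.** The Study Summary (Pharmacological challenge) sets the stagger: "Enrolment will be staggered so that each participant will start dosing at least 2 weeks after the previous participant". Its next sentences describe the safety visits: "Patients will be monitored for safety by clinic visit at the end of Weeks 2, 4, and 8".

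Section 4.1 sets the same interval. For the first pair: "The first patient will be followed for at least 2 weeks before the second patient starts the XBD173". For the others: "Subsequent participants will be treated with XBD173 90mg once daily for 2 weeks at intervals of at least 2 week".

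Section 6.4 places the Week 2 hospital visit within 3 days either side of its target. Appendix 1 shows haematology and clinical chemistry at screening and at Weeks 2, 4 and 8. The Week 1 contact (section 6.3) is a telephone call without bloods.

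Section 6.4 also links the Week 2 bloods to a dosing step: "Following completion of these procedures and review of the blood tests, the physician can increase the dose of XBD173 to 90mg twice daily". That step is the same participant's own dose increase, and by section 5.4 it does not apply to the first two: "Patient 3 onwards will escalating to 90mg twice daily after 2 weeks".

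**The concern.** A stagger in a small early-phase study is there so that what is learned from one participant can inform the decision to expose the next. Here the interval has the same nominal length as the time to the first on-drug safety bloods. Because the visit has a window and the stagger is a bare minimum in days, a site can follow the protocol exactly and still start the next participant before the bloods of the one before have been drawn or reported.

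This matters most for the first pair. Participant 1's Week 2 sample is the first scheduled on-drug laboratory information in this trial, in patients with PAH. It also comes after a longer exposure than any for which the protocol gives a duration. The longest is 7 days: "This study recruited healthy volunteers (n=31) and people with MS (n=12) and administered XBD173 90mg for 7 days". What could be missed for a few days is a laboratory change without symptoms, for example in transaminases, renal function or haemoglobin, all of which are used as exclusion criteria in section 4.3.2.

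**Working it through.** **Inputs**

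- Minimum interval between consecutive first doses: 14 days (Study Summary and section 4.1, which agree).
- Safety-blood visits: 14, 28 and 56 days after first dose, each ± 3 days (sections 6.4, 6.6 and 6.7; Appendix 1).
- Up to 6 participants (Study Summary).
- Laboratory turnaround T: not stated. Assumed 0 to 2 days; each further day adds one day to the gap.
- Also assumed: no discontinuation or replacement, and all visits held within their windows.

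**Earliest starts and the preceding Week 2 window**

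Let Day 0 be participant 1's first dose. Participant k starts at the earliest on Day 14(k − 1). The Week 2 draw of participant k − 1 falls between Day 14(k − 2) + 11 and Day 14(k − 2) + 17. An earlier draw counts as certain if the last day of its window is on or before the start day.

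| Participant | Earliest start | Preceding participant's Week 2 window | Earlier draws certain to have been taken |
|---|---|---|---|
| 2 | Day 14 | Days 11–17 | 0 |
| 3 | Day 28 | Days 25–31 | 1 |
| 4 | Day 42 | Days 39–45 | 3 |
| 5 | Day 56 | Days 53–59 | 5 |
| 6 | Day 70 | Days 67–73 | 8 |

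The counts arise as follows (P1 W2 is participant 1's Week 2 draw, and so on):

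- Participant 3: P1 W2, by Day 17. Total 1.
- Participant 4: adds P1 W4 and P2 W2, both by Day 31. Total 3.
- Participant 5: adds P2 W4 and P3 W2, both by Day 45. Total 5.
- Participant 6: adds P1 W8, P3 W4 and P4 W2, all by Day 59. Total 8.

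From participant 3 on, the latest certain draw precedes the start by 11 days (28 − 17, 42 − 31, 56 − 45, 70 − 59), which leaves ample time for a result.

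**Size of the gap**

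Latest result minus earliest next start = (17 + T) − 14 = 3 + T days. For T = 0, 1, 2 this is 3, 4 or 5 days, or about 3 to 5 once-daily doses of 90 mg. The window alone produces the 3 days, even with no turnaround. Elapsed time alone would guarantee the result only with a stagger of 17 + T days, that is, 17, 18 or 19.

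**When there is no gap**

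With the next start on Day 14, the result is late by max(0, visit day + T − 14) days:

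| Visit day | 11 | 12 | 13 | 14 | 15 | 16 | 17 |
|---|---|---|---|---|---|---|---|
| T = 0 | 0 | 0 | 0 | 0 | 1 | 2 | 3 |
| T = 1 | 0 | 0 | 0 | 1 | 2 | 3 | 4 |
| T = 2 | 0 | 0 | 1 | 2 | 3 | 4 | 5 |

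**Does another rule close the gap?**

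- The blood review in section 6.4 precedes the same participant's dose increase, not the next participant's start.
- Section 6.2 has results reviewed before first dose, but these are the participant's own pre-drug results.
- Section 9.1 has the site investigator review out-of-range results, with no timing relative to the next start.
- Section 11.6 stops further recruitment once certain events have occurred; it requires no review beforehand.

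None of these makes the next first dose depend on the preceding participant's Week 2 bloods.

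**The case against.** The protocol does not contradict itself: both statements of the stagger agree, and 2 weeks is a floor. The Study Summary puts the stagger beside the Week 2 visit, so the interval was plausibly meant to match it. The gap needs spacing at or near the minimum and a visit on about Day 14 or later. All of this stands, and it is why the point concerns what the rule permits. Plausible intent still does not bind a site, and the rule as written can be met without the visit having taken place.

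Other safeguards also stand. There is the Week 1 call, with a weight and ankle-swelling self-check (Appendix 1), and remote data are reviewed twice a week (section 4.1). Unscheduled bloods can be taken if clinically required (section 6.9), grade 2 adverse events lead to withdrawal (sections 4.1 and 4.3.4), and recruitment can be halted (section 11.6). These cover symptoms, haemodynamics and overt events. None requires a blood review before the next start.

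The exposure at issue is small. About 3 to 5 once-daily doses is less than the 7 days at 90 mg given to 31 + 12 = 43 people in a sponsor study, and section 4.1 reports the sponsor's studies as well tolerated with no SAEs. The protocol reports no laboratory signal; the side effects it names are nervous system and gastrointestinal. This limits the severity, although none of that experience is in PAH.

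Two stronger readings are tempting, and the document does not support them:

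- A reader might infer that no decision at all depends on the Week 2 bloods of participants 1 and 2. That cannot be said. Adverse events are graded by Appendix 2, a separate file not shown; if it grades laboratory changes, those bloods could trigger the grade 2 withdrawal rule.
- A reader might infer that all six participants are started without laboratory information. The counts above rule this out from participant 3 onwards.

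**Conclusion.** The concern holds, as a minor point. Followed exactly, the stagger allows participant 2 to start up to 3 days plus turnaround before any scheduled on-drug blood result exists in the trial; that is 3 to 5 days if turnaround is 0 to 2 days. For participants 3 to 6 only the immediately preceding participant's Week 2 result may be missing, at a once-daily dose already sampled in earlier participants, so the gap there carries little weight.

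It should not be read as saying that the gap will occur, that the step to twice daily lacks a blood review, or that any endpoint is affected. The sizes rest on minimum spacing, visits within their windows, no replacement, and the assumed turnaround. That the gap exists does not depend on turnaround, because the +3-day side of the window is enough.

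**What to change.** Amend the stagger sentence in the Study Summary and in section 4.1, for example:

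*A participant takes the first dose no sooner than 14 days after the participant before, and only once that participant's Week 2 safety bloods and adverse events have been reviewed. If that participant stopped before Week 2, the reason for stopping and all available safety data must have been reviewed instead.*

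The second sentence is needed because a participant withdrawn early may have no Week 2 bloods: section 4.3.4 provides a telephone assessment at 4 weeks, and section 4.3.5 requires a replacement. Without it the condition might never be met. If the sponsor wants the smallest change, applying the rule to participant 2 alone captures most of the benefit.

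The cost is one amended statement in each of two places and a delay of at most 3 + T days per pair when the Week 2 visit falls in its window. With T of 0 to 2 days that is 3 to 5 days for participant 2 alone. Over all five pairs it is at most 5 × 3 = 15 to 5 × 5 = 25 days, against a minimum of 70 days from first to last start, and only if every Week 2 visit falls on its last permitted day. Booking the visit on Days 11 to 13 reduces the delay to 0 or 1 day per pair.

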4.3.5 Subject identification and replacement policy

After informed consent is obtained, patients who are screened will be assigned a 7-digit permanent identification number (subject ID) such that all patients given consecutive identification numbers in successive order of inclusion. The first 4 digits of the will be the designated research site ID, and the last 3 digits will be assigned at the research study centre (e.g., if the site ID is 4410, the third patient screened at 4410 site, would be given the number 4410003).

A patient who is screened but fails to proceed into baseline assessment (e.g., because entry criteria were not met or enrolment did not occur within the specified time frame) may be considered for screening again. Re-screening will be permitted by the site Investigator on a case-by-case basis. A new informed consent form will be signed in any case of re-screening. A new subject ID will be assigned to the subject. Patients who are discontinued will be replaced. Each replacement is by a default a new subject, who will be assigned a completely new subject ID.

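### At a stagger of 14 to about 19 days, participant 4 may go to 90 mg twice daily before participant 3's Week 4 bloods and 12-lead ECG have been reviewed

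*Protocol*

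**What the plan says.** The study summary sets the spacing: "Enrolment will be staggered so that each participant will start dosing at least 2 weeks after the previous participant". Section 4.1 repeats the 2-week interval, again counted between starts of treatment.

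Participants 1 and 2 take 90 mg once daily throughout. For the next four, the summary says "XBD173 will be given orally 90mg once daily for the first 2 weeks", followed by 6 weeks of twice-daily dosing. Section 5.4 agrees: "Patient 3 onwards will escalating to 90mg twice daily after 2 weeks".

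The condition for going up is in section 4.1: "if the drug is tolerated (defined as an absence of grade 2 adverse events) the dose will be increased to 90mg twice daily". Section 6.4 adds that the physician may raise the dose once that participant's Week 2 procedures are complete and the bloods reviewed. Neither section mentions another participant's results.

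The first scheduled haematology, chemistry and 12-lead ECG after the increase come at Week 4 ± 3 days (sections 6.6 and 7.8, Appendix 1). Between the increase and Week 4 there is a telephone check at Week 3 (6.5) and twice-weekly review of remote data (4.1).

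On dose, section 4.1 says "The starting dose of 90mg OD is based on experience from studies of XBD173 in healthy volunteers and in patients with multiple sclerosis". The repeated-dose volunteer study it describes used "7 days treatment with placebo, 10, 30, or 90 mg/day XBD173".

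**The concern.** A stagger protects later participants only if something is learned in the interval. For once-daily dosing, it does. For twice-daily dosing, the first scheduled laboratory and 12-lead ECG data are participant 3's at Week 4. At the minimum stagger, that visit falls nominally on the same day as participant 4's Week 2 visit. As section 4.1 is worded, participant 4's dose goes up whatever participant 3's results show, and whether or not anyone has seen them.

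The step is a doubling to 180 mg a day, twice the highest human daily dose the protocol states. The cited experience is offered as support for the once-daily starting dose. What is at stake is one missed chance to see a silent laboratory or 12-lead ECG change in participant 3 before exposing a second patient to the same dose.

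**Working it through.** **Inputs from the protocol**
- Minimum interval between first doses: 14 days (study summary, 4.1). This is stated consistently, and there is no derived figure to reproduce.
- Once-daily lead-in: 2 weeks (study summary, 5.4). Week 2 visit: own day 14 ± 3 (6.4).
- Week 4 visit with bloods and ECG: own day 28 ± 3 (6.6, 7.8, Appendix 1).

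**Assumptions, because the protocol gives no figure**
- Laboratory turnaround *t* is 1 to 3 days, the same for both participants.
- The ECG is read at the visit.
- Nobody escalates before own day 14, following the 2-week lead-in.

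**Formulae.** Day 0 is participant 3's first dose, and participant 4 starts on day *S*.
- Participant 3's Week 4 visit: *v* = 25 to 31. The ECG is known on day *v* and the bloods on day *v + t*.
- Participant 4's Week 2 visit: *w* = *S* + 11 to *S* + 17.
- Participant 4's escalation: *e* = max(*S* + 14, *w + t*).
- Gap for bloods = *v + t − e*; gap for ECG = *v − e*. A positive gap means that escalation comes first.

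**Nominal case, *S* = 14.** Here *w* = 28, *v* = 28 and *e* = 28 + *t*.
- Bloods: (28 + *t*) − (28 + *t*) = 0 days.
- ECG: 28 − (28 + *t*) = −*t*, so it is known 1 to 3 days before escalation.

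**Worst case, *S* = 14.** Participant 4 is seen early (*w* = 25), so *w + t* is at most 28 and *e* = 28. Participant 3 is seen late (*v* = 31).
- Bloods: 31 + *t* − 28 = 4, 5 or 6 days for *t* = 1, 2 or 3.
- ECG: 31 − 28 = 3 days.

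**Opposite extreme, *S* = 14.** With *w* = 31, *t* = 3 and *v* = 25, *e* = 34, which is 9 days after participant 3's visit.

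**Staggers at which a gap is possible**
- Bloods: *S* + 14 < 31 + *t*, so *S* is at most 17, 18 or 19 for *t* = 1, 2 or 3. From 20 days there is none.
- ECG: *S* + 14 < 31, so *S* is at most 16. From 17 days there is none.

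**Without the day-14 floor.** If the ± 3 days at Week 2 are read as permission to escalate sooner, *e* = *w + t*.
- Bloods: the worst gap at *S* = 14 is (31 + *t*) − (25 + *t*) = 6 days for any *t*.
- ECG: 31 − (25 + *t*) = 5, 4 or 3 days.
- The blood gap still needs *S* + 11 < 31, so *S* is at most 19.

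**Other participants at the minimum stagger**
- Participants 5 and 6 escalate no earlier than days 28 + 14 = 42 and 42 + 14 = 56. Participant 3's results are in by 31 + 3 = 34, with margins of 8 and 22 days.
- Participants 1 and 2 started on days −28 and −14. On day 28 they are at days 56 and 42 of once-daily dosing, past their own Week 4 checks.

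**Dose.** 2 × 90 = 180 mg a day, and 180/90 = 2.

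**The case against.** The strongest reply is that nothing in the protocol is broken. It has two once-daily participants first, a 2-week lead-in for everyone else, review of own bloods before the increase, and stopping rules at grade 2. Section 6.4 says the physician can, not must, raise the dose, and at one centre the same team will probably know about participant 3. The overlap is also only permitted. The stagger is a minimum, and the recruitment rate is not given. Even at exactly 14 days, 18 of the 49 pairs of visit days leave a gap in bloods with a 1-day turnaround and 21 of 49 with a 3-day turnaround. The maximum of 4 days arises in 3 pairs and the maximum of 6 days in 1. These are counts, not probabilities. Finally, one participant's panel shows an effect of true frequency *p* only with probability *p*.

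All of that stands, and it keeps the point small. It does not remove it: section 4.1 says the dose goes up if that participant tolerates the drug, and nothing prompts a look at participant 3. The conditions in section 11.6 stop recruitment; they do not hold an increase in someone already enrolled.

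Three stronger readings are tempting but not supported.
- *No safety information on twice daily exists before participant 4 escalates.* The Week 3 call, remote rhythm and haemodynamic data and any unscheduled visit can give some. What may be missing is the first scheduled bloods and 12-lead ECG.
- *180 mg a day has never been given to humans.* Section 1.2 mentions development to Phase IIa without giving doses. The 90 mg ceiling is only what the protocol states, and it assumes that the 7-day study under 17/LO/0566 gave 90 mg a day.
- *All four escalating participants are exposed to the gap.* If participant 3 reaches Week 4, participants 5 and 6 are not.

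**Conclusion.** The point holds in a limited form. The stagger governs first doses, and escalation looks only at the participant's own data. Participant 4 may therefore double the dose before participant 3's Week 4 bloods and 12-lead ECG have been reviewed.

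This can happen only when participant 4 starts 14 to about 19 days after participant 3. Bloods and ECG should be kept apart: in the nominal case neither is late, and an ECG read at the visit has the shorter worst-case gap. The sizes rest on the assumed turnaround and the day-14 floor; dropping the floor raises the worst gap in bloods to 6 days at any turnaround. The numbering assumes that participant 3 does escalate; otherwise the roles move along.

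This is an inexpensive safety improvement to a workable design, not an error in it.

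**What to change.** Keep the 14-day stagger and add to sections 4.1, 5.4 and 6.4:

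> Escalation does not occur before day 14. After the first participant escalates to twice daily, no other participant escalates until the investigator has reviewed that participant's Week 4 haematology, chemistry and 12-lead ECG and found no grade 2 or higher change. If that participant stops twice daily before Week 4, the investigator reviews the reason for stopping and all available data, and, if escalation then goes ahead, the next participant to escalate takes over this role.

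The rule names the first participant to escalate because section 4.1 says "If a grade 2 AE occurs during 90mg once daily dosing, the participant will be withdrawn" and section 4.3.5 says "Patients who are discontinued will be replaced". A rule tied to participant 3 might never be met. The last sentence is needed because early discontinuation brings only a telephone follow-up (4.3.4), and unscheduled bloods and ECG are done only if clinically required (6.9). Results from the point of stopping cannot be relied on.

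**Cost.** There are no extra scheduled visits or samples and no change to enrolment dates. The nominal wait is 0 days, since participant 4's own bloods from the same day must be reviewed anyway. The worst case is about 4 to 6 days. If the Week 8 visit is kept, twice-daily dosing falls from 42 days to 42 − 4 = 38 or 42 − 6 = 36, a loss of 4/42 = 9.5% to 6/42 = 14.3%. If the first escalator stops early, the hold passes on and may delay a later participant.
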